6.1 Study Flowchart

See Appendix 1.

6.2 Informed Consent and Enrollment

Subjects will be requested to provide written informed consent (IC) after receiving the study information. The investigators will explain the materials according to the requirements of subjects. Every subject (or his/her legal representative) and investigator must sign and date the IC form (ICF) approved by the Institutional Review Board/Independent Ethics Committee (IRB/IEC) before the subject can proceed with the qualification screening. Copies of the ICF will be provided to all subjects. Subjects who provide written IC will be screened and evaluated. Subjects who do not provide IC will receive further treatment according to the doctor's advice and/or the subject's willingness.

After obtaining IC from subjects, the investigators shall screen them according to the inclusion and exclusion criteria, confirming that subjects do not fall under any of the exclusion criteria. Only when a subject meets all inclusion criteria and does not meet any exclusion criteria can the investigators assign the subject into a group according to the random assignment instruction.

6.3 Medical History and Vital Signs

During the screening visit, the medical history of the subjects will be collected and recorded in

the eCRF. Baseline measurements, including blood pressure and heart rate, will be taken.

6.4 Randomization

The assignment for each subject into either the control group (no MMA embolization) or the study group (MMA embolization) will be determined by the randomization scheme. SAS (version 9.4 or updated) is used to generate the randomization list by a stratified randomization method. During screening, a unique identification number (screening number) is allocated to each subject who has provided the signed ICF. The annotation for the screening number includes a subject number and site number (e.g., the first subject in 01 site is 01001). This digital ID is allocated according to the order of entry into the study after the subject signs the ICF at the study site.

On day 0 of the trial, subjects obtain the corresponding randomization numbers and will be randomized to the study group or the control group at a ratio of 1:1.

The randomization number of subjects in all study groups is designated as #: D-ZZZ

D = representing the treatment group; expressed with Arabic numerals 1-X, where 1 represents the study group and 2 represents the control group.

ZZZ=Subject digital ID

Treatment allocation in this study is not blinded.

6.5 Clinical Examination and Evaluation

(1) Inspection items before randomization include:

Routine blood work (red blood cell count, white blood cell count, platelet count, and hemoglobin);

Coagulation (activated partial thromboplastin time [APTT], INR);

Hepatic and renal function (alanine aminotransferase [ALT], aspartate aminotransferase [AST], blood urea nitrogen [BUN], creatinine [Cr]), electrolytes (potassium, sodium, chlorine, and fingerstick blood glucose);

Cranial CT scanning;

DSA;

Cranial MRI (depending on the conditions);

Urine human chorionic gonadotropin (HCG) test (female of childbearing age).

(2) Assess mRS score and EQ-5D score at screening and during baseline period;

(3) Total length of hospital stay, destination for rehabilitation after discharge, and total hospitalization expenses are recorded at discharge;

(4) Record severe surgery-related complications of subjects in 30 days after any surgical procedure (including burr-hole drainage and MMA embolization);

(5) Re-examine cranial CT/MRI at 90 days after randomization and record total hospital stay, re-hospitalization times, destination for rehabilitation after discharge, and total hospitalization expenses;

(6) Assess mRS score and EQ-5D score at 90 days and 360 days after randomization;

(7) Record SAEs, SDH-related death events, and severe surgery-related complications, total hospital length of stay, number of re-hospitalizations, destination for rehabilitation after discharge, and total hospitalization expenses at 30 days, 90 days and 360 days after randomization.

7. Statistical Analysis

7.1 General Principle

A biostatistician will develop a statistical analysis plan according to the study protocol before data locking.

Continuous variables are expressed as mean \pm standard deviation, with the number of cases, median, maximum, and minimum provided; categorical variables are described by frequency and constituent ratio.

7.1.1 Test level

Two-sided tests are performed for all hypothesis tests ($\alpha = 0.05$). The confidence level of all confidence intervals is 95%.

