Study Objectives	
Primary objective:
 
To validate that middle meningeal artery (MMA) embolization with liquid embolic materials, when compared to conventional treatments, can reduce the incidence of hematoma recurrence in patients receiving trepanation and drainage and the incidence of hematoma progression in patients undergoing conservative treatment in symptomatic non-acute subdural hematoma (SDH) patients.
 
Secondary objectives:
 
 a. To validate the safety and efficacy of MMA embolization with liquid embolic materials; b. To assess change in residual hematoma size at 90 days post-procedure in patients undergoing MMA embolization; c. To assess improvement in clinical outcome (modified Rankin Scale [mRS] score) at 90 days and 360 days post-procedure in patients undergoing MMA embolization; d. To assess improvement in health status (EQ-5D scale) at 90 days and 360 days post-procedure in patients undergoing MMA embolization; e. To assess the readmission rate within 90 days post-procedure in patients undergoing MMA embolization.
Study Design	Multicenter phase III prospective randomized controlled trial with open-label treatment and blinded outcome assessment
Number of Study Sites	30-40 domestic hospitals
Statistical Considerations and Sample Size	Assuming that the incidence of events in the traditional treatment group is 12% and the embolization group is 5%, with a power of 90% and an estimated 8% drop-out rate, approximately 722 subjects should be enrolled with a ratio of 1:1 between the embolization group and the traditional treatment groups.
Inclusion Criteria	
 1. Patients with symptomatic non-acute SDH with mass effect (i.e., chronic or subacute SDH) 
Mass effect refers to a shift in midline structure or deformation of local cerebral cortex due to SDH.
 
Symptomatic defined as neurological symptoms, such as headache, short-term cognitive dysfunction, language disorder or aphasia, gait instability, decreased muscle strength, sensory disturbances, epileptic seizure, etc.
 
 2. Age \geq 18 years; 3. Pre-morbid mRS score \leq 2; 4. Informed Consent Form (ICF) signed by patient or guardian.

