remain sparse and warrant further large-scale clinical studies for robust evidence.

Onyx™ Liquid Embolic System, a leading liquid embolic, comprises an ethylene-vinyl alcohol (EVOH) copolymer, dimethyl sulfoxide (DMSO) solvent, and micronized tantalum powder. Its non-adhesive nature prevents microcatheter and vessel adhesion, facilitating safer post-embolization catheter retraction. Each application of Onyx™ propels preceding agents deeper into smaller vessels beyond microcatheter reach, enhancing dispersal. Onyx™ received CE certification in Europe in 1999 and was initially approved for cerebral AVM endovascular embolization. Notably, Rajah et al.'s case series utilizing Onyx for MMA embolization via the radial artery pathway underscored its safety and efficacy in CSDH treatment.²¹

Although various studies endorse MMA embolization as an effective treatment for CSDH, most are confined to single-center, prospective cohort designs with diverse patient inclusion criteria and intervention approaches. There's a notable gap in high-level evidence validating MMA embolization's efficacy. The MAGIC-MT study aims to bridge this gap by rigorously assessing the efficacy and safety of MMA embolization in comparison to conventional CSDH treatments. Furthermore, it seeks to contribute significantly to the standardization of clinical treatment protocols for CSDH.

2. Clinical Study Objectives and Endpoints

Primary objective:

To validate that MMA embolization with liquid embolic materials, when compared to conventional treatments, can reduce the incidence of hematoma recurrence in patients receiving trepanation and drainage and the incidence of hematoma progression in patients undergoing conservative treatment in symptomatic non-acute SDH patients.

Secondary objectives:

- a. To validate the safety and efficacy of MMA embolization with liquid embolic materials;
- b. To validate a reduction in residual hematoma size at 90 days post-procedure in patients undergoing MMA embolization;
- c. To validate improvement in clinical outcome (modified Rankin Scale [mRS] score) at 90 days and 360 days post-procedure in patients undergoing MMA embolization;

- d. To validate improvement in health status (EQ-5D scale) at 90 days and 360 days post-procedure in patients undergoing MMA embolization;
- e. To validate a reduced readmission rate within 90 days post-procedure in patients undergoing MMA embolization.

The efficacy endpoints in this study include:

Primary efficacy endpoint:

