3.1 Overall Study Design

This is a multicenter, phase III, prospective, randomized, open-label, and parallel controlled clinical study with blinded outcome assessment. Approximately 722 cases will be included in this study in China, with a ratio of 1:1 for randomization into the MMA embolization and

traditional treatment groups.

The study phases include: 1) Screening and baseline period: confirm whether patients are eligible for the study and create a record; decide whether trepanation and drainage should be performed by considering the condition of the disease and the imaging results; carry out randomized assignment and therapy. Eligible subjects will be randomly assigned to the traditional treatment group or MMA embolization group at a ratio of 1:1. 2) Follow-up period: visit patients for efficacy endpoints and safety endpoints at 30 days, 90 days, and 360 days post-procedure.

Figure 1. Schematic diagram of inclusion and randomization of subjects

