7.1.3 Estimation of sample size

This study hypothesizes that MMA embolization may reduce the recurrence (operation group) or progression (conservative treatment group) of SDH. The estimated recurrence or progression rate of hematoma in the MMA embolization group is 5%, while that of control group is 12%. When estimating bilateral 5% for the statistical significance level, 90% for power, and 8% for an acceptable rate of loss to follow-up, the total sample size is estimated to be 722 cases.

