### **3. Sample Size Considerations**

The study hypothesizes that patients undergoing middle meningeal artery embolization may have lower symptomatic recurrence (in the trepanation/drainage group) and lower rates of symptomatic hematoma progression (in the non-surgical group) of subdural hematoma compared to patients who do not go MMA embolization. Two interim analyses will be conducted. With an expected symptomatic recurrence rate (trepanation/drainage group) / symptomatic progression rate (non-surgical group) after MMA embolization of 5% compared with 12% in the control group, and considering a loss to follow-up rate of 8%, a sample size of 722 cases with a two-sided alpha of 0.05 would yield 90% power.

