**Table 6 Planned Overview of Secondary Efficacy Endpoint Analyses**

	Data Presentation Generated		
	Table	Figure	Listing
Incidence of recurrence or progression of SDH at 360 days after randomization: Same as Table 4 Overview of planned primary statistical analyses			
Categorical secondary endpoints: Success rate of target blood vessel embolization in DSA imaging Change in mRS score at 90 days and 360 days after randomization compared to baseline Proportion of patients with mRS score of 0 to 2 at 90 days and 360 days after randomization Proportion of patients with mRS score of 0 to 3 at 90 days and 360 days after randomization Destination for rehabilitation after discharge (going home vs rehabilitation hospital)			
Statistical description of categorical data: Number (n) and percentage of subjects in each category			
Dichotomous data analysis: - Proportion and its 95% CI - Difference in sample rate between MMA embolization and control groups, p-value and 95% CI - OR for MMA embolization and control groups with 95% CI	Y		Y
Continuous Secondary Endpoints: Changes of hematoma thickness in CT or MRI imaging at 90 days after randomization compared to baseline Changes of hematoma volume at 90 days after randomization Changes of midline shift in CT or MRI imaging at 90 days after randomization Changes of mRS score at 90 days and 360 days after randomization Quality of life evaluated with EQ-5D-5L Scale at 90 days and 360 days after randomization Total hospital stay (number of days) Re-hospitalization times Total hospitalization expenses			
Statistical description of continuous data: - Number of non-missing cases (n) - Mean (standard deviation)	Y		Y

	Data Presentation Generated		
	Table	Figure	Listing

 
- Median
 
- Min, Max
 
- Q1,Q3
 
 
Continuous data analysis:
 
 
- Estimate of mean and 95% CI for MMA embolization and control groups
 
- Difference in means and 95% CI between MMA embolization and control groups
 
- P value for difference in means between MMA embolization and control groups
 
			

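### Sixteen to eighteen secondary between-arm tests, each at two-sided 0.05, serve objectives partly worded as validation, with no testing order, adjustment or exploratory label

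*Protocol*

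**What the plan says.** **Test level.** Protocol 7.1.1: "Two-sided tests are performed for all hypothesis tests", with alpha 0.05 and 95% confidence intervals throughout.

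**Secondary tests.** Protocol 7.3.2 plans a chi-square test or t-test between arms for the secondary endpoints. SAP Table 6 asks for a p-value for the dichotomous endpoints and, for the continuous ones, a "P value for difference in means between MMA embolization and control groups". SAP 9.1.2.2 assigns the methods: the primary-endpoint method for the 360-day event and other categorical endpoints, ordinal logistic regression for mRS, mixed models for thickness and volume, and t-tests for the remaining continuous endpoints.

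**Objectives.** Protocol section 2 has "To validate improvement in clinical outcome (modified Rankin Scale [mRS] score" where the synopsis has "To assess improvement in clinical outcome (modified Rankin Scale [mRS] score". The same change of verb runs through objectives b to e. SAP 1.2 follows section 2. Objective a says *validate* in both places.

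**Error control.** SAP section 2 states one pair of hypotheses, for the 90-day primary endpoint, and attaches its 0.05 rule to them. SAP 4.1 deals with type I error at the two interim looks. Neither document says anything about multiplicity among the secondary endpoints.

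**The concern.** A verb such as *validate*, combined with a 0.05 level for every test, invites the reader of the final report to treat a secondary result below 0.05 as confirmed. With this many tests and no rule, some such results are to be expected by chance. Nothing in the plan makes a secondary claim depend on the primary endpoint succeeding. The conclusions at stake are those on function, quality of life, residual hematoma and readmission. Because the synopsis uses the weaker verb, the documents also leave open whether these objectives are confirmatory at all.

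**Working it through.** **1. The plan's own figure.** The inputs are in Protocol 7.1.3: "The estimated recurrence or progression rate of hematoma in the MMA embolization group is 5%, while that of control group is 12"%, and "90% for power, and 8% for an acceptable rate of loss to follow-up, the total sample size is estimated to be 722 cases". Allocation is 1:1 (Protocol 3.1). With pooled variance, two-sided 0.05 and mean rate 0.085:

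n per arm = [1.9600 × √(2 × 0.085 × 0.915) + 1.2816 × √(0.12 × 0.88 + 0.05 × 0.95)]² / 0.07² = 331.5, rounded up to 332.

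Total 664; 664 / (1 − 0.08) = 721.7, rounded up to 722. This reproduces the plan's number and agrees with SAP section 3 ("a sample size of 722 cases with a two-sided alpha of 0.05 would yield 90% power"). The full 0.05 is spent on the primary endpoint, and nothing in the calculation concerns the secondary endpoints.

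**2. Number of secondary tests.** Each endpoint is counted once per time point, by one test, in the ITT set.

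| Endpoint | Tests |
|---|---|
| Recurrence or progression at 360 days | 1 |
| Thickness, volume, midline shift at 90 days | 3 |
| mRS change at 90 and 360 days | 2 |
| mRS 0 to 2 at 90 and 360 days | 2 |
| mRS 0 to 3 at 90 and 360 days | 2 |
| EQ-5D at 90 and 360 days | 2 |
| Hospital stay, re-hospitalizations, discharge destination, expenses | 4 |
| **Total** | **16** |

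SAP Table 6 lists mRS change under both the categorical and the continuous endpoints. If both analyses are run, two tests are added, making 18. Embolization success is left out because DSA is done only in the embolization group (Protocol Appendix 1, footnote e). Supporting models, subgroup analyses and per-protocol repeats are not counted.

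**3. Independent tests, all secondary nulls true.**

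- At least one p < 0.05 in either direction: 1 − 0.95^16 = 56.0%; 1 − 0.95^18 = 60.3%.
- At least one favouring embolization (0.025 per test): 1 − 0.975^16 = 33.3%; 1 − 0.975^18 = 36.6%.
- Expected number of false positives: 16 × 0.05 = 0.8 to 18 × 0.05 = 0.9 in either direction; half of that, 0.4 to 0.45, favouring embolization.

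**4. Correlated tests.** The documents give no correlations, so these are assumptions. Test statistics were simulated as Z = √ρ × C + √(1 − ρ) × E, where C is shared by all tests and E is separate for each (200,000 replicates).

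| Assumed ρ | 16 tests: either direction / favouring embolization | 18 tests: either direction / favouring embolization |
|---|---|---|
| 0.3 | 47.7% / 24.6% | 51.0% / 26.3% |
| 0.5 | 37.4% / 18.8% | 39.7% / 19.9% |
| 0.7 | 26.2% / 13.1% | 27.8% / 13.9% |
| 0.9 | 14.6% / 7.3% | 15.1% / 7.6% |

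A block structure with 16 tests (0.7 within imaging, 0.8 within mRS, 0.7 within EQ-5D, 0.5 within hospital use, 0.2 between blocks) gave 41.8% / 21.7%, inside the same range.

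**5. With control.** A fixed sequence gated on the primary keeps each test at 0.05 and the chance of any false claim in the sequence at or below 0.05.

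**The case against.** Secondary endpoints are commonly read as supportive. The plan states formal hypotheses only for the primary endpoint, and Table 6 sets no success rule. The verb *validate* also covers safety, where SAP 9.2 plans summaries and listings without between-arm tests, so it is not the plan's term for p < 0.05. This stands in part. A reader might infer that any single secondary result below 0.05 counts as validated under the plan, but no passage says so. The defect is that the plan does not say how such a result is to be read, and Protocol 7.1.1 together with the objectives points towards the confirmatory reading.

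The count can also be pushed too far in either direction. A reader of Table 6 might infer eight mRS tests and a fixed total of 18. However, SAP 9.1.2.3 names mRS change as the endpoint of the ordinal model and omits mRS from its continuous list, which supports six mRS tests and 16 in total. In the other direction, objective e names only the readmission rate. Leaving out stay, destination and expenses gives 13 tests, and 1 − 0.975^13 = 28% favouring embolization if independent. SAP 1.2 does list those three as endpoints for that objective, so they remain in the count here.

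Nor is the whole set necessarily tested twice. SAP section 5 drops the extra per-protocol efficacy analyses if that set holds at least 90% of the full set and the difference is expected to be negligible.

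**Conclusion.** The point holds as a gap in the plan: 16 to 18 unadjusted secondary tests at 0.05, with contradictory wording on whether the objectives are confirmatory. If no secondary effect exists, the chance of at least one false result in favour of embolization is up to 33 to 37% under independence and about 13 to 26% at assumed common correlations of 0.3 to 0.7. That is roughly 5 to 10 times the 2.5% of a single test.

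A reader might infer from the 56 to 60% figure that a false validation is more likely than not. It is not. That figure requires independent tests and counts results against embolization as well. The endpoints are plainly related: three measures of the same hematoma, several cuts of mRS at two times, and quality of life beside them. All the figures assume that every secondary null is true.

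The primary test, its alpha and the sample size of 722 are not affected. The change is worth making because it determines what may be concluded from the secondary results.

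**What to change.** 1. In SAP 9.1, state that secondary endpoints are reported as estimates with 95% CIs, labelled as not adjusted for multiplicity, and without claims of significance. This should cover the 360-day event too, because it falls under objective a, which says *validate* in both protocol places.
2. For any secondary endpoint the sponsor wants to claim, prespecify a short fixed sequence before unblinded results are seen. Test it only if the primary endpoint is significant, and stop at the first non-significant result. The choice and order of endpoints belong to the sponsor.
3. In Protocol section 2 and SAP 1.2, replace *validate* by *assess* for objectives b to e, as in the synopsis.
4. State in the SAP whether mRS change is analysed once (ordinal) or also as a continuous variable, so that Table 6 and 9.1.2.3 agree.

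The cost is wording in the SAP and protocol, with no new data and no change in sample size. The downside is that endpoints outside the sequence cannot be claimed as significant, however small their p-values.

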7.1.2 Hypothesis test

Original hypothesis: there is no difference in the incidence of recurrence or progression of hematoma between the MMA embolization group and the traditional treatment group at 90 days post-procedure;

Alternative hypothesis: there is a difference in the incidence of recurrence or progression of hematoma between the MMA embolization group and the traditional treatment group at 90 days post-procedure.

7.1.3 Estimation of sample size

This study hypothesizes that MMA embolization may reduce the recurrence (operation group) or progression (conservative treatment group) of SDH. The estimated recurrence or progression rate of hematoma in the MMA embolization group is 5%, while that of control group is 12%. When estimating bilateral 5% for the statistical significance level, 90% for power, and 8% for an acceptable rate of loss to follow-up, the total sample size is estimated to be 722 cases.

7.1.4 Estimation of missing values

Missing values are not imputed.

7.1.5 Subject disposition

Description of subjects' enrollment, drop-out cases, completion of expected follow-up, and early suspension presented as the number of cases and percentage;

Subject disposition by data set.

Descriptions for drop-out subjects are individually described, including treatment condition, reason for premature withdrawal from the trial, etc.

7.1.6 Protocol violation and deviation

Summarize and describe the subjects with protocol violations and deviations.

7.1.7 Demographics and baseline characteristics

Age, height, weight, vital signs, and other baseline characteristics are described by mean, standard deviation, median, maximum, and minimum; the constituent ratio is calculated for

gender, smoking status, drinking status, medical history, drug allergy history, physical examination, etc.

